The untrained subjects, who have never used either of the systems previously, will be sequestered in such a way that they cannot observe or be influenced by the testing technique of other study participants. They will learn to use the assigned meter by reading the corresponding User Guide (UG) and Quick Reference Guide (QRG). Each subject will perform one fingerstick self-test using a Microlet NEXT or similar lancing device and the assigned meter. Immediately following the subject self-test, a Tenderlett™ or similar device will be used by the study staff on the subject's finger (same hand) to collect a capillary sample for testing on the YSI Glucose Analyzer.

Immediately following the Tenderlett lancing, subjects will lance their palm using the Microlet NEXT lancing device (with AST clear endcap) and will perform a self-test using the meter.

Immediately following the AST test, the staff person will perform a fingerstick test on the subject. All subject self-test results and study staff results will be compared to YSI results from blood obtained from the Tenderlett fingerstick.

Hematocrit will be measured for all subjects.

All Subjects will then complete a questionnaire (Questionnaire 1) to provide feedback on the meter system and instructions for use (UG and QRG).

Procedures - Only Subjects with Diabetes

Subjects with diabetes will be given a venipuncture. The venous blood will be tested by the study staff using the CONTOUR NEXT and CONTOUR TV3 systems, maintaining randomized first meter order, and the YSI lab analyzer. The venipuncture may be performed any time after the subject is enrolled (i.e. completed informed consent and passed inclusion/exclusion criteria).

After all testing is completed, staff will demonstrate to the subjects with diabetes several features of the meter system that would not necessarily be experienced during the brief accuracy testing. These subjects will be given a second questionnaire (Questionnaire 2) to provide feedback about the new features of the system.

Procedures repeated with second BGMS

After completing study procedures for one BGMS, subjects will then repeat all of these procedures using the second BGMS, except the hematocrit and venipuncture procedures. (Hematocrit is measured on a separate instrument and is not meter-specific; venipuncture is performed once and measured on both meters, as previously described.)

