5.5 Study Staff Quality Control Testing of Meters

Prior to enrollment of the first subject, the study staff will perform testing with Contour normal level control solution on all CONTOUR NEXT and CONTOUR TV3 meters. All staff control testing will be done out of sight of the study subjects. If the results are out of range, troubleshooting will be performed (see meter UGs) and the test will be repeated. If the meter tests are out of range after troubleshooting is complete, the meter will be removed from the study. This will be documented on the Problem Reporter form, as described in Section 5.15 'Device Problem Reporting'.

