5.7 Tests (See Table 5.2 for test scheme.)

Each subject will be provided with all the materials needed for self-testing during the visit: one CONTOUR NEXT meter, one CONTOUR TV3 meter, a Microlet NEXT or similar lancing device, lancets, Contour NEXT test strips, V3 test strips, CONTOUR NEXT and CONTOUR TV3 UGs and QRGs. The subject will be given time to review the UG and QRG to learn how to use the system but no training will be provided.

The subject will wash his/her hands thoroughly with warm water and soap, rinse and dry well.

5.7.1 **Fingerstick Testing**

1. The subject will perform a fingerstick using the Microlet NEXT lancing device and test his/her blood on Meter 1. The study staff person will record the time and test result of the successful meter test on the appropriate form. For instructions on handling error codes and repeat testing, refer to protocol section 5.10 'Errors'.
2. Immediately, but at least within 5 minutes of the fingerstick self-test, the study staff person will lance the subject's finger (preferably the same hand as above) with a Tenderlett device in order to collect enough blood for testing on the YSI Analyzer (approx. 200–300 uL). The time of this Tenderlett lancing will be recorded.
3. If adequate blood is not obtained from the Tenderlett lancing, 2 additional Tenderlett lancements are allowed (total of up to 3 Tenderlett lancements). The blood is to be combined into one tube for YSI analysis.
4. The blood sample will be centrifuged as soon as possible after sample collection but not longer than 15 minutes after the meter test. The study staff person will record the time of centrifugation.
5. In order to reduce glycolysis of the plasma, it is recommended that the plasma be transferred from the microtainer tube to a micro/dispo tube or similar container, prior to analysis on the YSI Analyzer.
6. The plasma sample will be assayed on the YSI Analyzer: 1 sip = 1 result from black probe and 1 result from white probe. See 5.12.3 for details on testing of plasma samples.

7. Immediately following the subject plasma sample, a serum control close to the level of the subject plasma will be tested. (No re-calibration is required). The serum control test result should be within the range shown in Table 5.1. See 5.12.3 for details.
8. Additional details regarding processing of blood samples for the YSI Analyzer are found in Appendix B.

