5.7.3 Study Staff test

1. Immediately following the AST testing, the study staff person will perform a fingerstick lancing using the same Microlet lancing device (new lancet) on the subject, preferably on the same hand as the other fingerstick lancing.
2. The staff person will test the fingerstick blood using the same meter and test strip lot used by the subject.
3. The study staff will record the time of the meter test. The time interval between the blood centrifugation and the final staff meter test should be as soon as possible, and within 15 minutes or less.
4. If the time from meter test to blood centrifugation exceeds 15 minutes, the test is considered non-evaluable. This will not be considered a protocol deviation. Times of meter tests and centrifugation will be recorded.

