5.14 Procedures repeated on BGMS 2

After completing study procedures for the first BGMS randomly-assigned to them, subjects will then repeat all of these procedures using the second BGMS, except the hematocrit and venipuncture procedures. (Hematocrit is measured on a separate instrument and is not meter-

specific; venipuncture is performed once and measured on both meters, as previously described.) Therefore, for BGMS 2, subjects will complete a fingerstick test; a YSI sample will be collected by a Tenderlett stick from subject; subject will complete a palm AST; study staff will perform a fingerstick test from the subject; study staff will administer Questionnaire 1; and, if the subject has diabetes, study staff will administer Questionnaire 2.

Table 5.2 – Subject Testing Schematic

Step	BGMS	Test type	Operator	Description
1	1	Fingerstick Self-test	Subject	
 ▪ Subject lances finger – Microlet NEXT lancing device. ▪ Test meter with 1 lot of test strip (Repeat 2 more times, only if needed). ▪ Record time of successful meter test.
2	1	Tenderlett deep stick	Study staff	
 ▪ Immediately following Step 1 meter test (≤ 5 min), staff lances subject fingertip (up to 3 lancements allowed). ▪ Record time of lancing. ▪ Collect blood in Li Heparin tube (approx. 200 – 300 uL). ▪ Centrifuge blood and record time (should be within 15 min of meter test in step 1).
3	1	AST palm Self-test	Subject	
 ▪ Immediately following Step 2, subject lances palm – Microlet NEXT lancing device. ▪ Test with same test strip lot and meter as above. (Repeat 2 more times, only if needed.) ▪ Record time of successful meter test (should be within 15 min of centrifugation in Step 2).
4	1	Study staff test	Study staff	
 ▪ Immediately following Step 3, staff lances subject fingertip - Microlet NEXT lancing device. ▪ Test with same test strip lot and meter as above. (Repeat 2 more times, only if needed.) ▪ Record time of successful meter test (should be within 15 min of centrifugation in Step 2).

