5	1 then 2	Venous test (only subjects with diabetes)	Study staff	
 ▪ May be done prior to Steps 1-4. ▪ Staff performs venipuncture on subjects with diabetes (up to 3 attempts allowed). ▪ Collect blood in 4 ml Vacutainer tube with heparin anticoagulant. ▪ Staff tests blood (out of view of subject) with same meter and strip lot as fingerstick test. ▪ Centrifuge blood and record time (should be within 15 min of venous blood meter test).
6	na	Hematocrit	Study staff	
 ▪ Fill 2 microhematocrit tubes (only 1 tube to be measured). ▪ Blood is from capillary or venous blood.
7	na	Questionnaire 1	Study staff	
 ▪ Study staff administers Questionnaire 1 to all subjects.
8	na	Questionnaire 2 (only subjects with diabetes)	Study staff	
 ▪ Study staff demonstrates BGMS features to subjects with diabetes. ▪ Study staff administers Questionnaire 2 to subjects with diabetes.
9-14	2	all	all	
 ▪ Repeat steps 1 – 4 (meter tests) and 7-8 (questionnaires) with BGMS 2.

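### Table 5.2 puts the first meter's staff fingerstick and demonstrations before the untrained self-tests on the second meter, and no analysis by meter order would show any carry-over

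*Combined protocol and SAP*

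**What the plan says.** **No training.** Section 5.7 gives subjects the User Guide and Quick Reference Guide "to learn how to use the system but no training will be provided". Section 3.0 calls them untrained and sequesters them so that they "cannot observe or be influenced by the testing technique of other study participants".

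**Order of steps.** In Table 5.2, steps 1 to 8 are completed on the first meter. Step 4 is the staff fingerstick: "Immediately following Step 3, staff lances subject fingertip - Microlet NEXT lancing device". Section 5.7.3 adds: "The staff person will test the fingerstick blood using the same meter and test strip lot used by the subject". Step 7 is Questionnaire 1; section 5.13.1 has staff demonstrate an error message to any subject who did not meet one. Step 8, for subjects with diabetes, is the feature demonstration followed by Questionnaire 2. Steps 9-14 then read "Repeat steps 1 – 4 (meter tests) and 7-8 (questionnaires) with BGMS 2". Section 5.14 and the last paragraph of section 3.0 give the same order in words.

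**Timing of the feature demonstration.** Section 3.0 says: "After all testing is completed, staff will demonstrate to the subjects with diabetes several features of the meter system". Section 5.13.2 is similar and adds that the first questionnaire must also be complete.

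**Shielding elsewhere.** For the venous test, Table 5.2 step 5 says: "Staff tests blood (out of view of subject) with same meter and strip lot as fingerstick test". For meter quality control, section 5.5 says: "All staff control testing will be done out of sight of the study subjects". Step 4 and section 5.7.3 carry no such condition.

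**Analysis.** Section 11.1 and Tables 11.2 and 11.3 report accuracy by site and combined. Nothing is planned by meter order.

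**The concern.** The fingerstick, palm and Questionnaire 1 objectives (2.1.1, 2.2.1, 2.2.2, 2.3.1) ask whether lay users relying only on the printed instructions reach fixed pass marks. For whichever meter comes second, the subject may already have seen trained staff lance, handle a strip and apply blood, and has been shown an error message or features of the first meter. If any of this helps, second-meter results no longer describe an untrained user.

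Randomised order protects a comparison between meters, but none is planned. Each meter is judged against an absolute mark, so a second-use gain is averaged into both meters' results. With no breakdown by order, it would also go unseen.

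**Working it through.** **1. Is the sequence as described?** Steps 9-14 are 14 − 9 + 1 = 6 steps. The steps to be repeated are 1-4 (four) and 7-8 (two), also 6. So the table is internally consistent, and the second meter's self-tests follow the first meter's steps 4, 7 and 8.

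**2. Do text and table conflict?**
- If all testing means both meters, sections 3.0 and 5.13.2 put the demonstration after step 12 (the second meter's staff test), while Table 5.2 also has one at step 8. They conflict.
- If it means testing on the current meter, all passages agree. Section 3.0 follows directly with the instruction to repeat everything on the second system, and section 5.14 repeats Questionnaire 2. The exposure before the second meter is then planned.

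Section 5.13.1 ties Questionnaire 1 to the individual meter's testing, whereas 5.13.2 uses the broader term, so the wording does not settle it.

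**3. How many results are exposed?** The allocation ratio for order is not stated; 1:1 is assumed. Then 350 / 2 = 175 results per meter are second-use. The feature demonstration reaches only subjects with diabetes, 85-90% of enrolment: 0.85 × 175 ≈ 149 to 0.90 × 175 ≈ 158.

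**4. The plan's own figures.** With n = 350 and 333 required, the exact binomial P(X ≥ 333) is 0.9500 at 96.65%. The chance of failing is 0.9495 at 92.81%. Both match section 11.1.

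**5. What could a gain do?** Let X1 ~ Bin(175, p) be first-use results within ±15% and X2 ~ Bin(175, p + d) second-use results. The pass probability is P(X1 + X2 ≥ 333), by convolution. The documents give no value for d, so 0 to 4 points is an assumed range, as are the first-use rates of 94% and 95%.

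| First-use p | d = 0 | 1 pt | 2 pts | 3 pts | 4 pts |
|---|---|---|---|---|---|
| 92.81% | 0.0505 | 0.0988 | 0.1785 | 0.2965 | 0.4500 |
| 94% | 0.2190 | 0.3516 | 0.5147 | 0.6855 | 0.8327 |
| 95% | 0.5148 | 0.6852 | 0.8319 | 0.9312 | 0.9806 |

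Here d is the whole second-use gain. It includes what subjects learn from their own first-meter tests, so staff exposure accounts for some unknown part of it.

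**6. What could an analysis by order show?** For one meter, first-use and second-use results come from different subjects. At 95% accuracy in each half, the standard error of the difference is √(2 × 0.95 × 0.05 / 175) = 0.0233, so a 95% interval is about ±1.96 × 2.33 = ±4.6 points. It would reveal a large carry-over but could not exclude one of 2 points.

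**The case against.** The strongest reply is that no rule is broken. Read per meter, sections 3.0, 5.13.2, 5.14 and Table 5.2 agree. The demonstrated features are, by 5.13.2, ones that accuracy testing would not necessarily touch, and they belong to the first meter, not the one tested next. Nothing says the error-message demonstration shows technique. Table 5.2 is silent on whether the subject watches step 4. All of this stands. Only the staff fingerstick plausibly displays testing technique.

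The shielding parallels are also imperfect. The section 5.5 control tests precede enrolment of the first subject. The venous test may come before any self-test, so it has a stronger reason to be hidden; the staff fingerstick always follows both self-tests on its own meter. This weakens the parallel but does not answer the point about the second meter.

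Further, subjects have by then practised on the first meter, most have diabetes, and untrained here means new to these two systems, not to all meters. That limits the gain attributable to staff. If true accuracy is near the plan's 96.65%, the pass chance is already about 95% and there is little left to inflate.

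Finally, step 4 uses the subject's own finger, directly after the palm test and within a 15-minute limit, so full concealment may not be practical. That is fair, and the fix allows for it.

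**Conclusion.** The point holds as a carry-over risk, together with one phrase that needs defining. About half of each meter's self-test and Questionnaire 1 data, if order is 1:1, come after unshielded staff handling and demonstrations on the other meter, and the planned analysis could not show whether that mattered. The size is unknown and may be zero. The table above shows only how sensitive the 333/350 rule is to an assumed gain that mixes staff exposure with practice.

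A reader might infer that Table 5.2 contradicts the no-training rule and the stated timing of the demonstration, or that subjects do watch the staff test and are shown correct technique. The documents do not support this. The timing conflicts only if all testing means both meters, the no-training rule is not literally breached, and the step 4 text neither says subjects watch nor prevents it. Nor can it be said that results are inflated, only that they could be. The change is worth making because it is nearly free and the exposure bears on the untrained-user objectives.

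**What to change.** 1. State in sections 3.0 and 5.13.2 that all testing means the tests on both meters. Re-sequence Table 5.2 and section 5.14 so that both feature demonstrations and both administrations of Questionnaire 2 follow the second meter's tests.
2. In step 4 and section 5.7.3, require staff strip and meter handling to be out of the subject's view where feasible.
3. Limit any error-message demonstration given before second-meter testing to the display, with no testing technique. It must stay before Questionnaire 1, which asks about error messages.
4. In section 11, add accuracy and Questionnaire 1 results by meter order (first-used versus second-used) as a sensitivity analysis with confidence intervals. Label it descriptive, given the ±4.6 points above.

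The cost is protocol wording, a screen or similar arrangement at step 4, and a few extra tables from data already collected. No sticks or subjects are added. The drawback is that Questionnaire 2 for the first meter is answered slightly later; it has no pass/fail criterion.

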5.15 Device Problem Reporting

Any functional problems with the CONTOUR NEXT or CONTOUR TV3 BGMS will be documented by the study staff. The study staff should be specific about describing the problem and the sequence of events that led to it. All information will be documented on the Problem Reporter Form, including the meter type, serial number and test strip lot. Malfunctioning BGMS will be replaced and this will be documented for study tracking. If appropriate, such meters will be disinfected and shipped back to Ascensia for evaluation.

5.16 Temperature and Humidity Monitoring

The study staff will measure the temperature and humidity of the meter and YSI testing area(s) twice a day (AM and PM) using an audited thermometer/hygrometer supplied by Ascensia, and record the results on the appropriate form.

5.17 Miscellaneous

Ascensia representatives may observe subject visits as part of study staff training, study monitoring or for troubleshooting problems with the investigational devices. This will be done under supervision of the investigator.

Ascensia representatives may assist with disinfection of the meters, and perform centrifugation of blood samples and measurement of hematocrit.

Ascensia representatives will not train or interact in any way with the subjects. The presence of Ascensia representatives will be noted in the ICF.

Subjects will receive nominal compensation for their time and inconvenience.

6.0 Risk / Benefit Assessment

Risks associated with this study include those associated with obtaining blood from finger, palm and venipuncture.

The following risks are anticipated and will not be reported as Adverse Events (AE). (See section 7.0 for further details.)

- 1) Bleeding: Mild bleeding similar to being stuck with a pin
- 2) Swelling (Edema): A mild swelling similar to a mosquito bite
- 3) Bruising: Less than one inch across (fingerstick) or less than 2 inches across (venipuncture)
- 4) Redness (Erythema): Mild reddening or darkening of the skin in the immediate area around the puncture site
- 5) Soreness: Mild discomfort at the puncture site resolving (going away) within one to two days (fingerstick or palm) or within hours (venipuncture)

The following risks are unlikely, but possible, and will be reported as anticipated Adverse Events:

- 1) Bleeding: Continued bleeding requiring changing a bandage
- 2) Bruising: A worsening bruise that is firm to the touch

- 3) Redness (Erythema): Bright redness or skin darkening spreading across the area (fingerstick or palm) or across the arm (venipuncture)
- 4) Soreness: Worsening pain and/or pain that interferes with activity
- 5) Infection: Bright redness or skin darkening spreading across the area with warmth and/or swelling, and/or red streaking
- 6) Nerve injury: Numbness or shooting pain in the forearm
- 7) Numbness in the area of the puncture wound
- 8) Dizziness
- 9) Fainting

Subjects should be instructed to report such events to the investigator or designee.

Benefits

A benefit associated with the study is the sense of well-being gained by contributing to the development of improved or new blood glucose monitoring systems, which may be beneficial to people with diabetes or other diseases or conditions.

7.0 Adverse Event Management and Medical Device Reporting

The procedures to be performed under this protocol are considered to be low risk.

7.1 Description and Classification

7.1.1. An AE during a clinical evaluation is “any untoward medical occurrence, unintended disease or injury, or untoward clinical signs (including abnormal laboratory findings) in subjects, users or other persons, whether or not related to the investigational medical device.” It is not dependent on whether the event is considered to be related to the investigational product or the study. An AE includes events not seen at the beginning of the study, or worsened if present at the beginning. Adverse events can be classified as presented in Table 7.1.

7.1.2. The next classification to consider is whether or not the AE is Anticipated or Unanticipated. In order for an AE to be considered ‘anticipated’ it must be listed in the protocol and ICF prior to any occurrence.

7.1.3. For studies on products that have not yet been cleared for market, it is important that all AEs be documented and included in the study file.

7.1.4. An unanticipated adverse device effect (UADE) is: Any serious adverse effect on health or safety or any life-threatening problem or death caused by, or associated with a device, if that effect, problem or death was not previously identified in nature, severity or degree of incidence in the investigational plan or application (including a supplementary plan or application), or any other unanticipated serious problem associated with a device that relates to the rights, safety or welfare of subjects [21CFR812.3(s)].

7.1.5. All AEs observed by the Investigator or reported by the subject will be documented on the AE form (including all symptoms) and included in the study file.

7.2 Events related to hypoglycemia and hyperglycemia

Hypoglycemia and hyperglycemia can be a common occurrence with subjects who have diabetes.

If it is found that a subject has a hypoglycemic event, as determined by the Principal Investigator (PI) during a study visit, the subject will be treated by the site staff accordingly. Appendices D and E note each site’s treatment plan.

Classification of the hypoglycemic or hyperglycemic event is at the discretion of the PI or designee. If the hypoglycemic or hyperglycemic event is considered by the PI as an AE, it will be considered to be an anticipated AE and will be recorded on the AE Form.

Subjects who are hypo- or hyperglycemic may continue with fingerstick testing if they so choose, and if the PI determines that it is safe. The PI will define what is considered to be a hypoglycemic or hyperglycemic state.

Table 7.1: Classification of Adverse Event

Serious*	Non-Serious

An adverse event that leads to:
 
 a) death; b) a serious deterioration in health of the subject that, 
 1) resulted in a life-threatening illness or injury, 2) resulted in a permanent impairment of a body structure or a body function, 3) required in-patient hospitalization or prolongation of existing hospitalization, 4) resulted in medical or surgical intervention to prevent permanent impairment to body structure or a body function; c) fetal distress or a congenital abnormality or birth defect. 
May be anticipated or unanticipated.
 
*EN ISO 14155. Clinical investigation of medical devices for human subjects – Good Clinical Practice
	
All adverse events not reported as serious. At each visit, all adverse events observed by the investigator/designate or reported by subject must be evaluated and recorded on an adverse event form.
 
A non-serious adverse event is further classified with respect to severity and relationship to the trial product. A non-serious adverse event may be anticipated or unanticipated.
 
Further classification with regard to severity
 
 • Mild: Transient symptoms, easily tolerated, no interference with subjects daily activities. • Moderate: Marked symptoms, moderate interference with subjects daily activities, and tolerable. • Severe: Considerable interference with subject’s daily activities, not tolerable.

Relationship to trial product:
 
 • Definitely Related: Causal relationship has been established and documented • Probably Related: Good reasons and sufficient documentation to assume causal relationship have been established • Possibly Related: Causal relationship is likely and cannot be excluded • Probably Not Related: Good reasons and sufficient documentation not established to assume causal relationship • Not Related: The event is most likely related to an etiology other than the trial treatment 	

